7.2 Secondary Endpoints

7.2.1 Time to stable INR

The time to stable INR is defined as the number of days from randomisation to attaining therapeutic INR for two consecutive measurements that are at least 7 days apart. Patients who were lost to follow-up or did not achieve stable INR during the observation period would be censored at their last follow-up visit. The comparison between study groups will be described using the Kaplan Meier curves and the logrank test. The effect estimate will be quantified using the hazard ratio (HR) and its associated 95% CI.

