2.1 Changes to Study Protocol

The SAP summarises the statistical design and methodologies presented in the April 2014 version of the study protocol; and where differences exist, supersedes the study protocol. Any changes to the study protocol as listed in this SAP have been submitted to and approved by the Domain Specific Review Board (DSRB) of the National Healthcare Group (NHG). Any differences with the study protocol are clearly described, and the rationale for the amendments explained.

3. Study Objectives

The primary objective is to assess the clinical benefits of genotype-guided dosing of warfarin against the traditional mode of dosing which uses only clinical factors.

The secondary objective is to prospectively evaluate the accuracy and precision of the pharmacogenetic dose-prediction model used to calculate the maintenance dose for patients in the pharmacogenetics arm [1].

4. Study Design

This is a multicentre, open-label, randomised controlled trial which uses a noninferiority study design. Patients newly indicated for warfarin therapy will be randomised 1:1 to receive pharmacogenetics-guided or the traditional dosing regimen. The therapeutic International Normalised Ratio (INR) range is considered to be >1.9 and \leq 3.1.

The disposition of patients who were screened for eligibility will be summarised in a CONSORT flow diagram [2].

Protocol Version and Date: Version 13, April 2014 SAP Version and Date: Version 1, June 2016

5. Sample Size Calculation

The sample size of 270 (135 in each study arm) provides 80% power to detect a non-inferiority margin of 0.5 with a one-sided alpha of 0.05, given a betweengroup difference in mean number of dose titrations of 1.0 and common standard deviation of 1.4. Primary analysis will use the intention-to-treat population, which will include patients evaluable for the primary endpoint at 12–14 days

Assuming an attrition rate of 15% after randomisation, approximately 320 patients would be enrolled and randomly allocated in a 1:1 fashion to the study groups.

6. Reporting of Patients Baseline Characteristics

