4.2 Study Design

Study endpoints and Statistical Considerations Refer to Appendix 4 – Statistical Analysis Plan

Accrual of study subjects with new indication for warfarin therapy (n = 350)

Informed consent

Patient Randomization; Determination of target therapeutic INR

Traditional dosing regimen

Pharmacogenetics-guided dosing

Dose Initiation Regimen (first 3 days)			
	Traditional dosing regimenPharmacogenetics-guided dosing		
Day 1	Low-molecular weight heparin	Low-molecular weight heparin	
Day 2	Low-molecular weight heparin	Low-molecular weight heparin	
Day 3	Low-molecular weight heparin Warfarin 5mg	Low-molecular weight heparin Warfarin tailored dose (if pharmacogenetics results available)	
Day 4	Low-molecular weight heparin Warfarin 4mg if age >75 years All others 5mg	Low-molecular weight heparin Warfarin tailored dose (if pharmacogenetics results available)	
Day 5	Low-molecular weight heparin Warfarin 3mg	Low-molecular weight heparin Warfarin tailored dose (if pharmacogenetics results available) Switch to standard protocol if pharmacogenetics results not available by day 5	
Day 6	Low-molecular weight heparin Check INR Warfarin dose according to Appendix 1A For all subsequent INRs checked during dose initiation phase, Warfarin dose will be determined by Appendix 1B	Low-molecular weight heparin Warfarin tailored dose (if pharmacogenetics results available) Check INR if three doses of warfarin had been administered, and dose subsequent warfarin dose according to Appendix 2A. For all subsequent INRs checked during dose initiation phase, Warfarin dose will be determined by Appendix 2B	
7-9 days after initiation of warfarin	INR check	INR check	
12-14 days after initiation of warfarin	INR check	INR check	

* Once therapeutic INR is achieved, low-molecular heparin should be stopped, and INR should be re-checked at least once within a week (this may coincide with the INR check on day 7-9 or day 12-14)

Maintenance Dose Regimen

- Once INR is maintained within the target range of 2-3 for 2 or more consecutive checks without a change in dose for at least 3 months, patients are considered to have reached maintenance dose.
- The total period of follow up for this study is approximately 3 months
- The number and frequency of visits should be between 3 to 5 during the first 2 weeks of initiating therapy although more visits may be required depending on the individual patient's response to warfarin therapy.

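### Time to stable INR: death, and permanent warfarin discontinuation after which visits end, are censored, so the Kaplan-Meier curve overstates the share reaching stable INR (minor, secondary endpoint)

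*SAP*

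**What the plan says.** SAP 7.2.1 defines the endpoint as "the number of days from randomisation to attaining therapeutic INR for two consecutive measurements that are at least 7 days apart". The censoring rule is a single sentence: "Patients who were lost to follow-up or did not achieve stable INR during the observation period would be censored at their last follow-up visit". On analysis it states: "The comparison between study groups will be described using the Kaplan Meier curves and the logrank test". It adds: "The effect estimate will be quantified using the hazard ratio (HR) and its associated 95% CI".

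On duration, protocol section 4.2 says: "The total period of follow up for this study is approximately 3 months". The only figure for losses is in SAP section 5: "Assuming an attrition rate of 15% after randomisation, approximately 320 patients would be enrolled". That figure covers all causes and is not broken down.

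SAP 7.2.1 mentions neither death nor permanent discontinuation of warfarin, and plans no cumulative incidence estimate. Both kinds of event are foreseen elsewhere, without rates. Protocol 4.9.1 lists death among the serious adverse event criteria, and protocol 4.7 refers to adverse events that lead a subject to leave the study early.

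**The concern.** A patient who dies cannot go on to record two therapeutic INRs a week apart. Nor, in any useful sense, can a patient who has stopped warfarin permanently. Under 7.2.1 such a patient has not achieved stable INR and is censored at the last visit.

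Kaplan-Meier redistributes a censored patient's weight over those still at risk, which assumes that the patient would have stabilised later at their rate. For a patient who can no longer stabilise, that assumption is false, and the error always raises the curve.

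At stake is the absolute reading of the curve: what share of each arm reached stable INR, and by when. It is the only absolute description planned for this endpoint. The separate percentage endpoint in the SAP executive summary concerns target INR by days 12-14, which is a different quantity. If one arm lost clearly more patients to death or permanent stopping, its curve would be raised more than the other's.

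**Working it through.** The SAP gives no event rate, hazard ratio or power for this endpoint, so there is no figure of its own to reproduce. The check asks how far one minus Kaplan-Meier lies above the true share.

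**Inputs from the documents**
- Endpoint, censoring rule and estimator: SAP 7.2.1.
- Follow-up of about 3 months, taken as 90 days: protocol 4.2.
- Total attrition of 15%: SAP section 5. It serves only as a ceiling on the assumed rates.
- 320 patients randomised 1:1, so 160 per arm: SAP section 5.

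**Assumptions, not in the documents**
- F1, the true share reaching stable INR by day 90: 50% to 80%.
- F2, the share who first die, or stop for good and are no longer seen: 1% to 15%.
- Constant cause-specific hazards over the 90 days.

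**Formula**
- Total cumulative hazard: H = -ln(1 - F1 - F2).
- Part belonging to stable INR: H1 = H × F1 / (F1 + F2).
- With the other events censored, 1-KM = 1 - exp(-H1).
- Overstatement = (1-KM) - F1.

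**Worked case, F1 = 60%, F2 = 5%**
- H = -ln(0.35) = 1.050.
- H1 = 1.050 × 0.60 / 0.65 = 0.969.
- 1-KM = 1 - exp(-0.969) = 62.1%, which is 2.1 points too high.

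**Overstatement per arm, percentage points**

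| True share F1 | F2 = 1% | 2% | 5% | 10% | 15% |
|---|---|---|---|---|---|
| 50% | 0.3 | 0.6 | 1.6 | 3.4 | 5.4 |
| 60% | 0.4 | 0.8 | 2.1 | 4.4 | 7.0 |
| 70% | 0.5 | 1.0 | 2.6 | 5.5 | 9.0 |
| 80% | 0.6 | 1.2 | 3.2 | 7.1 | 12.0 |

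The last column would need the whole of the assumed attrition to be death or permanent stop, which nothing in the documents supports.

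**Check by simulation** (400,000 patients, weekly visits, no other loss to follow-up)
- F1 near 60%, F2 = 5%: true share 59.9%. Kaplan-Meier gives 62.1% when these patients are censored at their last visit, and 59.9% when they stay at risk, event-free, to about day 90.
- F1 near 70%, F2 = 15%: true share 70.0%, against 79.5% and 70.0%.

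**Timing of the competing events.** At F1 = 70% and F2 = 5%, constant hazards give 2.6 points. In a separate simulation, events confined to days 0-30 gave about 3 points and events spread over days 0-90 gave 1.6.

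**Between-arm difference.** The same formula is applied to each arm. SE is the binomial standard error of a difference between two arms of 160, for example √(2 × 0.6 × 0.4 / 160) = 5.5 points when both true shares are 60%.

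| True shares | F2 by arm | Shift in difference | Shift / SE |
|---|---|---|---|
| 60% vs 70% | 5% vs 5% | 0.5 points | 0.10 |
| 60% vs 60% | 3% vs 5% | 0.9 points | 0.16 |
| 70% vs 70% | 3% vs 5% | 1.1 points | 0.21 |
| 60% vs 60% | 2% vs 8% | 2.6 points | 0.48 |
| 70% vs 70% | 2% vs 8% | 3.3 points | 0.65 |

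**The case against.** The strongest reply is that the rule censors at the last follow-up visit, not on the day warfarin stops. A patient who stops but keeps attending to 3 months therefore stays in the risk set without an event and is counted correctly. So is a patient who is hard to titrate but completes follow-up. No section says that visits end when warfarin ends. This stands: the bias is confined to deaths and to stoppers whose visits also end.

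It also stands that the planned test and effect estimate are sound. Logrank and hazard ratio with these events censored are cause-specific comparisons, and the SAP does not commit to reporting one minus Kaplan-Meier as a percentage. Only the absolute reading of a descriptive curve is affected.

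It stands as well that the size is unknown and may be small. The protocol excludes patients judged unfit for warfarin, which may limit early stopping, though that is inference.

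A reader might infer more: that every patient failing to stabilise is wrongly removed from the risk set, that the treatment comparison is invalid, or that the arm with more bleeding or failed titration is necessarily flattered. The documents support none of these. Completers without stable INR are properly censored at the end of follow-up, and nothing in the documents indicates that death or stopping differs between arms.

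The reply does not remove the remaining fault. As worded, the rule censors deaths, and the bias for them runs in one direction only.

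**Conclusion.** The point holds in a limited form. For patients who die, or who stop warfarin permanently and are not seen again, the rule in 7.2.1 makes the Kaplan-Meier curve overstate the share reaching stable INR. The direction is certain but the size cannot be fixed from the documents: no rate of either event is given, and reading these events into the catch-all sentence is itself an interpretation, since the SAP does not name them.

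With assumed true shares of 50% to 80% and constant hazards, a rate of 2% or less costs at most about 1.2 points per arm. Effects of several points need a rate nearer 10%. At equal or similar rates in the two arms the difference between them shifts by about a point or less, and it took a fourfold imbalance (2% against 8%) to move it by about half a standard error. The endpoint is one of nine secondary endpoints, and the primary analysis of dose titrations is untouched. This is a minor correction.

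**What to change.** In SAP 7.2.1:

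- Name death and permanent discontinuation of warfarin before stable INR as competing events.
- Show cumulative incidence (Aalen-Johansen) curves by arm in place of one minus Kaplan-Meier. Keeping such patients event-free in the risk set to the end of the 3-month follow-up gives the same share when there is no other loss, as in the simulation above.
- Keep the logrank test and hazard ratio, computed with competing events censored when they occur, and label them as cause-specific. If the risk set is extended for the curve, do not run these two on the extended set, because they would no longer be cause-specific.
- Censor only true loss to follow-up and the end of follow-up.
- Gray's test is optional. If it is added, state in advance which test governs.

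The cost is a few sentences and a few lines of code. The data needed are the date of death and the date and reason for ending warfarin. No treatment, visit or sample size changes. The downside is that the reported share reaching stable INR becomes slightly lower.

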7.2.2 Number of dose adjustments at 1, 2 and 3 months

The total number of dose adjustments per patient will be tabulated at the end of every month. This endpoint will be analysed using repeated measures analysis via a mixed model with Poisson link function, and will be reported as an incidence rate ratio (IRR).

7.2.3 Number of INR assessments at 1, 2 and 3 months

The total number of INR assessments per patient will be tabulated at the end of every month. The analysis will be performed using a mixed model in the same manner as endpoint 7.2.2.

7.2.4 Proportion of patients whose INR exceeded 3.0

This endpoint will compare the fraction of patients who experienced an INR > 3.0 at any time point while on the trial. The risk ratio and its 95% CI will be used to quantify the effect size between study groups, and the P-value will be calculated using the Chi-square test.

7.2.5 Frequency of bleeding episodes

The number of patients who experienced a bleeding event during the dosetitration phase, which will be classified as major or minor, as described by Levine et al [3] will be tabulated for each study group. The risk ratio and its 95% CI will

Protocol Version and Date: Version 13, April 2014 SAP Version and Date: Version 1, June 2016 be used to quantify the effect size between study groups, and the P-value will be calculated using the Chi-square test.

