2.1 Changes to Study Protocol 3. Study Objectives	
4. Study Design	.3
5. Sample Size Calculation	.4
6. Reporting of Patients Baseline Characteristics	.4
7. Study Endpoints	.4
 7.1 Number of dose titrations performed up to days 12-14 7.2 Secondary Endpoints	.4 .5 .5 .5 .5 .6 .6
7. References	. /

1. Executive Summary

Title	A Randomized Controlled Trial to Assess the Clinical Benefits of a			
	Pharmacogenetics-Guided Dosing Regimen for Calculating			
	Warfarin Maintenance Dose			
Sponsor	National Medical Research Council			
Principal Investigator	[name].			
Study Agent	Warfarin (Marevan®)			
Study Design	This is a multicentre, open-label, randomised (1:1) controlled trial			
	which uses a non-inferiority study design.			
	Primary analysis will be based on intention-to-treat.			
Sample Size	The sample size of 270 provides 80% power to detect a non-			
	inferiority margin of 0.5 with a one-sided alpha of 0.05, given a			
	between-group difference in mean number of dose titrations of 1.0			
	and common standard deviation of 1.4.			
	Assuming an attrition rate of 15%, 320 patients would be enrolled			
	and randomly allocated 1:1 to a study group.			
Interim Analysis	None			
Patients	Eligible patients must be at least 18 years of age; have a new			
	indication for warfarin; have no previous history of liver disease,			
	malabsorption syndrome or chronic diarrheal conditions; do not			
	have uncontrolled hypertension, peptic ulcer disease or any			
	medical condition deemed unfit for warfarin therapy.			
Drimony Objective	Written informed consent is required prior to enrolment. To compare pharmacogenetics-guided versus traditional dosing of			
Primary Objective	warfarin in terms of anticoagulation control parameters			
Treatment Duration	Patients will be followed for 3 months from treatment initiation			
Primary Endpoint	 Number of dose titrations performed up to days 12-14 			
Secondary Endpoints	2. Time to stable INR*			
	3. Number of dose adjustments at 1, 2 and 3 months			
	4. Number of INR assessments at 1, 2 and 3 months			
	5. Proportion of patients whose INR exceeded 3.0			
	6. Frequency of bleeding episodes			
	7. Incidence of recurrent venous thromboembolism with 90 days			
	of diagnosis			
	8. Percentage of patients achieving target INR by days 12-14*			
	9. Percentage of time spent within therapeutic INR range*			
	10. Accuracy (MPE%) and precision (RMSE%) of the			
	pharmacogenetic maintenance dose-prediction model			

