7.1 Number of dose titrations performed up to days 12-14

The primary endpoint is the number of dose titrations performed up to 12-14 days following the initiation of warfarin therapy. The average number of dose titration will be compared between study groups using the Student's t-test.

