7.2.6 Incidence of recurrent venous thromboembolism within 90 days of diagnosis

The number of patients who were indicated for warfarin therapy due to venous thromboembolism (VTE) who experienced recurrence within 90 days of diagnosis will be tabulated for each study group. The risk ratio will be used to compare the effect size between study groups, and the P-value will be calculated using the Chi-square test.

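### SAP 7.2.5 limits the bleeding comparison to a dose-titration phase that is never defined; depending on the reading it excludes about 0% to 87% of follow-up and may or may not differ by arm

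*SAP*

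**What the plan says.** SAP 7.2.5 tabulates, by study group, the patients who "experienced a bleeding event during the dosetitration phase", classified as major or minor. The risk ratio and its 95% CI are to "be used to quantify the effect size between study groups, and the P-value will be calculated using the Chi-square test". Nothing adjusts for time at risk.

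The Executive Summary lists the endpoint only as "Frequency of bleeding episodes", with no window. It gives the treatment duration as "Patients will be followed for 3 months from treatment initiation". Protocol section 4.2 agrees: "The total period of follow up for this study is approximately 3 months".

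The only time limit placed on titration belongs to another endpoint, in SAP 7.1: "The primary endpoint is the number of dose titrations performed up to 12-14 days following the initiation of warfarin therapy". The nearest phase term in the protocol text, "For all subsequent INRs checked during dose initiation phase" (section 4.2), also has no stated end.

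For recurrent VTE, SAP 7.2.6 says: "The risk ratio will be used to compare the effect size between study groups, and the P-value will be calculated using the Chi-square test". Unlike 7.2.4 and 7.2.5, it mentions no confidence interval.

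**The concern.** Bleeding and recurrent VTE are the only clinical events among the listed endpoints. Bleeding alone is confined to an unspecified part of follow-up: INR above 3.0 is counted at any time on trial, VTE recurrence over 90 days, and dose adjustments to month 3.

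Two things are at stake. A short window would leave most of the follow-up time out of the bleeding comparison. A window that closes when a patient stabilises would close at a time the intervention is meant to change, so a risk ratio on patient counts would mix bleeding rate with length of observation. Because the phase is undefined, the choice could also be made after the data are seen, in an open-label trial.

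**Working it through.** The plan gives no bleeding rate, expected count or power for this endpoint, so there is no figure of its own to reproduce. Bleeding risks and response-dependent window lengths below are assumptions.

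**Inputs from the documents.** Follow-up 3 months, taken as 90 days (Executive Summary; protocol 4.2). Primary-endpoint window 12-14 days (SAP 7.1). 135 patients per arm, 270 in total, and one-sided alpha 0.05 (SAP 5). Stable INR: two successive in-range values a week or more apart (SAP 7.2.1). Maintenance dose: in-range INRs with the dose unchanged for 3 months or longer (protocol 4.2).

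**Step 1. Share of follow-up left out, 1 − window/90.**

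| Reading of the phase | Window | Left out | Can differ by arm? |
|---|---|---|---|
| (a) Primary-endpoint period | 12 days | 1 − 12/90 = 87% | No |
| | 14 days | 1 − 14/90 = 84% | No |
| (b) Until INR or dose is stable | 28 days (assumed) | 69% | Yes |
| | 42 days (assumed) | 53% | Yes |
| | 60 days (assumed) | 33% | Yes |
| (c) Until protocol-defined maintenance dose | 90 days | about 0% | No |

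Reading (c) leaves out essentially nothing because a milestone that needs 3 months without a dose change cannot be reached before a follow-up of about 3 months ends. These are shares of time, not of bleeds; if bleeding is more frequent early, the share of bleeds lost is smaller.

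**Step 2. Effect of unequal windows under reading (b).** With the same constant hazard h in both arms and windows t₁ (pharmacogenetic) and t₂ (traditional):

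RR = [1 − exp(−h·t₁)] / [1 − exp(−h·t₂)], close to t₁/t₂ when bleeds are rare.

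For an assumed 90-day risk of 10%, h = −ln(0.90)/90 = 0.00117 per day. The risks are 0.0163 at 14 days, 0.0243 at 21, 0.0322 at 28 and 0.0480 at 42.

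- 21 vs 28 days: 0.0243/0.0322 ≈ 0.75
- 28 vs 42 days: 0.0322/0.0480 ≈ 0.67
- 14 vs 28 days: 0.0163/0.0322 ≈ 0.50
- Equal windows (14 vs 14, or 90 vs 90): 1.00

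Assumed 90-day risks of 5% and 20% change these by less than 0.01. The direction favours whichever arm titrates faster.

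**Step 3. Information lost with a short window.** Expected patients with a bleed among 270, equal hazards:

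| Assumed 90-day risk | 14 days | 28 days | 90 days |
|---|---|---|---|
| 5% | 2.1 | 4.3 | 13.5 |
| 10% | 4.4 | 8.7 | 27 |
| 20% | 9.2 | 18.1 | 54 |

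Power for a true risk ratio of 0.5 at 135 per arm is Φ(z), where z = [|p₁ − p₂|√n − 1.645√(2p̄(1 − p̄))] / √[p₁(1 − p₁) + p₂(1 − p₂)]. For control risks derived from 5%, 10% and 20% at 90 days, it is 11%, 15% and 22% with a 14-day window, against 29%, 47% and 75% with 90 days.

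**Step 4. Sparse tables.** Halving the Step 3 counts gives the expected number per arm. At 14 days it is 1.1, 2.2 and 4.6, below 5 in every case; at 90 days it is 6.75, 13.5 and 27. So the window largely determines whether chi-square is strained for all bleeds together. Major bleeds alone would be fewer. For VTE, the expected count falls below 5 when risk is under 5/n; with an assumed subgroup of 80 per arm that is 5/80 = 6.25%. The documents give neither the subgroup size nor an event rate.

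**The case against.** A reader might infer that the window is response-dependent, drops most of follow-up and therefore biases the risk ratio towards pharmacogenetic dosing. The text does not say so. It sets no rule for ending the phase, and the one place that puts a time limit on titration (SAP 7.1) uses a calendar period equal in both arms, which creates no exposure bias. Unequal windows and loss of most of follow-up occur together only under reading (b) with a window shorter than about 45 days. Reading (b) is still natural, since the appendices separate an initiation phase from a maintenance phase with no changeover day and the plan's stability milestones rest on INR. It is one reading among three.

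A reader might also call this the main safety comparison behind a non-inferiority claim. The margin applies to the number of dose titrations; bleeding is a secondary endpoint with no margin. Other safety information is kept: INR above 3.0 over the whole trial, VTE over 90 days, and serious adverse event recording (protocol 4.9.1 and 4.11).

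Finally, chi-square cannot be called wrong on the documents alone. No event rates are given, and minor bleeds count towards 7.2.5.

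These objections limit the claim. They do not supply a definition, explain why bleeding has a narrower window than its neighbours, or add an adjustment for time at risk.

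**Conclusion.** The point holds in this form: the bleeding window is undefined, narrower in wording than the 3-month follow-up, and out of line with 7.2.4 and 7.2.6. Under the two readings in which the restriction has any effect, it either leaves out about 84-87% of a 90-day follow-up equally in both arms, or can make the unadjusted risk ratio follow window length (about 0.75 to 0.50 for the assumed pairs). Under the third it does nothing. Bias towards the pharmacogenetic arm is possible but not established. The 84-87% rests on the documents' own periods, with 3 months taken as 90 days; the risk ratios, counts and power rest on assumed window lengths, assumed risks and a constant hazard.

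Two minor points stand beside it: 7.2.6 lacks the confidence interval that 7.2.4 and 7.2.5 specify, and neither 7.2.5 nor 7.2.6 says what to do if the tables are sparse.

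**What to change.** Redefine 7.2.5 as patients with at least one bleed, reported as major and as minor, from warfarin initiation to the end of the 3-month follow-up, with the same window in both arms and analysis by assigned arm. State the denominator, because SAP 5 restricts the primary population to patients evaluable at 12-14 days. Put the same window in the Executive Summary. Keep the titration-phase count as a description only, with its end given as a calendar day.

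In 7.2.6, add the 95% CI for the risk ratio. For 7.2.5 and 7.2.6, state that an exact test is used when any expected cell count is below 5.

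The cost is mainly SAP wording, with one condition. The protocol explicitly requires recording of serious adverse events (section 4.11), but its data-collection section (4.3) does not list bleeding. The sponsor must therefore confirm that minor bleeds were captured throughout follow-up. If they were not, compare major bleeds over 3 months and minor bleeds over the fixed calendar window, and say so.
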